6.9 Criteria for Removal from Treatment

A patient's ongoing treatment on protocol will be temporarily or permanently withheld if any of the events below occur:

- 6.9.1. Illness that prevents further administration of treatment
- 6.9.2. Radiation dose constraints that are unable to be met at the current dose level.
- 6.9.3. DLTs or other unacceptable adverse events

- 6.9.4. Patient decision to withdraw from study
- 6.9.5. General or specific changes in patient's condition render the patient unacceptable for further treatment in the judgment of the treating physician or the study investigators

The reason for treatment stop/study removal and the date will be documented in a Case Report Form.

7. Measurement of Treatment

7.1 Toxicity Assessment

- 7.1.1. Dose-limiting toxicity (DLT) will be defined as grade 4 non-hematologic/grade 5 toxicity attributable to treatment, occurring until 30 days after ablation. Patients will be monitored and assessed for unexpected long-term toxicity during the post-treatment followup period. In the case of unexpected long-term toxicity, the dose level will be evaluated and potentially used to recalculate the MTD. Potential toxicities due to stereotactic body radiation therapy and microwave ablation are listed in Section 13.1 and 13.2 respectively. The most likely acute side effects of treatment include fatigue, nausea, vomiting, and pain due to the procedure. Toxicities not caused by treatment, such as pain due to tumor progression, will be excluded from the assessment.

7.2 Local Control

- 7.2.1. Imaging response will be measured as per the RECIST criteria[17]
 - 7.2.1.1. Complete Response (CR) – Disappearance of entire target lesion
 - 7.2.1.2. Partial Response (PR) – At least a 30% decrease in the sum of the diameters of the target lesion, taking as reference the baseline sum diameters.
 - 7.2.1.3. Progressive Disease (PD) - At least a 20% increase in the sum of diameters of target lesions, taking as reference the smallest sum on study (this includes the baseline sum if that is the smallest on study). In addition to the relative increase of 20%, the sum must also demonstrate an absolute increase of at least 5 mm. (Note: the appearance of one or more new lesions is also considered progression)
 - 7.2.1.4. Stable Disease (SD) - Neither sufficient shrinkage to qualify for PR nor sufficient increase to qualify for PD, taking as reference the smallest sum diameters while on study.

- 7.3 Progression free survival defined with follow-up radiological assessment with progression free survival (PFS) calculated from the point of start of SBRT to the point of recurrence or death.
- 7.4 Overall survival (OS) defined from the point of start of SBRT to the time of death or last follow-up if alive.
- 7.5 Tumor pathology: H&E staining and pathologic evaluation for percentage of viable tumor remaining as measured by the presence of necrosis, fibrosis, hyalinization, and/or calcification, compared to pre-SBRT pathology.

8. Study Parameters

- 8.1 Patients will be followed for a minimum of three years with standard-of-care clinical visits, laboratory studies, and imaging. A study calendar is provided below. After treatment, patients will be seen for clinical follow-up at 1 month after treatment and then every 3 months until 6 months after treatment, at which point the visits will occur every 6 months until 3 years have passed, at which point further follow-up will be at the discretion of the treating physician.

Table 2: Study Calendar

	Pre-treatment (within 6 weeks of reg)	Wk 1	Wk 2	4-6 wk post SBRT	MWA ¹	1 month post MWA	Follow up visits ²
Informed Consent	X						
Biopsy ⁴	X						
MRI Clearance	X						
Radiation planning	X						
SBRT		X	X				
Microwave Ablation					X		
Demographics	X						
Medical History	X	X				X	X
Physical Examination	X		X	X		X	X
Vital Signs	X			X		X	X
Height	X						
Weight	X		X			X	X
ECOG Performance status	X	X	X	X		X	X
Complete blood count with differential count	X		X	X			
Basic Metabolic Panel	X			X		X	X
Adverse event evaluation		X	X	X		X	X
B-hCG for WOCBP	X						
Research Biopsy ³	X				X		
Radiological evaluation/CT or MRI of Chest, Abdomen and Pelvis	X			X ⁵			X ⁵

¹: MWA will be approximately 8 weeks post XRT

²: Followup: 3 months and 6 months post MWA then every 6 month for 3 years, then annually

³: Research biopsy sampling will be done at the time of the diagnostic biopsy (if not yet performed at time of consent) and at during the microwave ablation procedure

⁴: Clinical diagnostic biopsy does not have a “window”. Patient must be treatment naïve for the renal cell carcinoma at time of study enrollment.

⁵: Imaging post ablation therapy will be at MD discretion, and in accordance with NCCN guidelines

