6.5 Microwave ablation (MWA)details

All procedures will be performed under sedation utilizing ultrasound and computed tomography (CT) guidance for percutaneous antenna placement and confirmation. A multidisciplinary team, consisting of a radiologist and a urologist experienced in tumor ablation, will perform each procedure. Depending on the size and location of the tumor, one to three antennas (Certus 140; NeuWave Medical, Madison, WI) will be used. The MW

system used for this study is the Certus 140 (NeuWave Medical, Inc., Madison, WI). The system is an FDA-approved, high-powered (140W in up to three channels) third-generation MW device that uses CO₂ gas cooling to prevent shaft heating. The gas cooling also allows the probes to be stuck into tissue by creating a small ice ball at the tip using the Joule–Thomson method, similar to the tissue cooling mechanism of cryoablation systems. The probes are 17-gauge, and several different ablation zone configurations are available depending on which probe is selected. The expected ablation diameter in ex vivo tissue is available on the manufacturer’s website (www.neuwave.com), but varies somewhat depending on the tissue type and tumor vascularity. If the tumor is in close proximity to adjacent structures, injectable grade dextrose 5% sterile water will be instilled through a spinal needle to increase the distance from the treatment zone (hydrodisplacement). For hydrodisplacement, the treatment team will consider the subjective proximity of structures as well as the expected ablation zone, which varies according to the manufacturer’s specifications for the individual probe types. An ablation protocol utilizing the 65W power setting for 5 minutes will be used in the majority of patients. Ultrasound will be used for real-time monitoring of the extent of ablation to achieve a 5mm margin beyond the tumor, and immediate post-procedure imaging performed using contrast-enhanced CT (CECT) for all patients with adequate renal function. All patients will be admitted overnight for observation as per standard of care.

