9.3 Definition of end-points

- 9.3.1 Primary Endpoint of the Phase I study:

Dose-limiting toxicity (DLT) will be defined as grade 4 or higher non-hematologic toxicity attributable to treatment occurring until 30 days after ablation. This will exclude toxicities not caused by treatment, such as pain due to tumor progression. Toxicities will be defined per NCI CTCAE v5.0.

- 9.3.2 Secondary endpoints of the Phase I study:
 - 9.3.2.1 Local control: Radiologic response per RECIST criteria and volumetric measurements.
 - 9.3.2.2 Progression free survival defined with follow-up radiological assessment with progression free survival (PFS) calculated from the point of start of SBRT to the point of recurrence or death.
 - 9.3.2.3 Overall survival (OS) defined from the point of start of SBRT to the time of death or last follow-up if alive.
 - 9.3.2.4 Tumor pathology: H&E staining and pathologic evaluation for percentage of viable tumor remaining as measured by the presence of necrosis, fibrosis, hyalinization, and/or calcification, compared to pre-SBRT pathology.

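### Local control is scored by RECIST against a pre-ablation diameter with no post-ablation reference, so if the whole ablation zone is measured, a successful ablation can be classed as progression when the nadir sum is 50 mm or less

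*Combined protocol and SAP*

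**What the plan says.** - **Progression rule.** Section 7.2.1.3: "At least a 20% increase in the sum of diameters of target lesions, taking as reference the smallest sum on study". The baseline can be that reference ("this includes the baseline sum if that is the smallest on study"), and there is an absolute limb: "the sum must also demonstrate an absolute increase of at least 5 mm". Complete response (7.2.1.1) requires the whole target lesion to disappear.
- **Endpoint.** Section 9.3.2.1: "Local control: Radiologic response per RECIST criteria and volumetric measurements". No volumetric cut-off is given. Section 9.4.2.1 reports local control actuarially without naming the RECIST category that counts as failure.
- **Ablation target.** Section 6.5: "Ultrasound will be used for real-time monitoring of the extent of ablation to achieve a 5mm margin beyond the tumor".
- **Scans.** Before MWA there is a pre-treatment scan and one at 4-6 weeks after SBRT (6.3, 6.7, Table 2). At the procedure, Section 6.5 specifies "immediate post-procedure imaging performed using contrast-enhanced CT (CECT) for all patients with adequate renal function". Follow-up imaging begins at 3 months under Section 6.8, although Table 2 footnote 5 leaves post-ablation imaging to physician discretion. The Table 2 row "Radiological evaluation/CT or MRI of Chest, Abdomen and Pelvis" has no mark under MWA.
- **PFS.** Sections 7.3 and 9.3.2.2 count recurrence or death. Recurrence is not defined and is not tied to RECIST progression.

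No section resets the RECIST reference at ablation, assigns the post-procedure CT to an endpoint, or says what is measured once the lesion has been ablated.

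**The concern.** Ablation deliberately creates a treated volume larger than the tumour. A diameter rule anchored to the smallest pre-ablation sum can then read the intended margin as growth. The plan neither excludes that reading nor supplies another: one reader may measure the zone, another only enhancing tissue, and they could reach opposite classifications for the same patient.

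The estimate at stake is local control. Section 9.1.2.1 gives the ten-patient Phase IB cohort the job of providing preliminary local control rates for a possible Phase II study, and Section 9.5.1 would power that study for a 15% increase over historical control. Because local control is reported actuarially, a false early event is not undone by later stable scans.

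**Working it through.** The plan states no figure on this point, so there is none to reproduce. The check is geometry.

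**Inputs from the protocol**
- Relative limb 20% over the nadir; absolute limb 5 mm (7.2.1.3).
- Margin 5 mm beyond the tumour (6.5).
- Tumour larger than 40 mm at entry (4.1.3). Metastatic patients are eligible (4.1.7), so the sum may hold other lesions.

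**Assumptions, not in the protocol**
- The whole zone is measured as the target lesion.
- The margin applies at both ends of the diameter: 2 × 5 = 10 mm.
- One target lesion, no zone shrinkage by the scan, and no tumour change between the nadir scan and ablation.

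**Base case.** For nadir d (mm), zone diameter = d + 10. The relative limb needs 10/d ≥ 0.20, so d ≤ 50 mm. The absolute limb is met, since 10 ≥ 5.

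| Nadir | Zone | Increase | Progression limit (1.2d) | Excess over limit | Progression? |
|---|---|---|---|---|---|
| 41 | 51 | 24.4% | 49.2 | 1.8 mm | yes |
| 45 | 55 | 22.2% | 54.0 | 1.0 mm | yes |
| 50 | 60 | 20.0% | 60.0 | 0.0 mm | yes, on the limit |
| 51 | 61 | 19.6% | 61.2 | -0.2 mm | no |
| 60 | 70 | 16.7% | 72.0 | -2.0 mm | no |

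A larger tumour enters the range only if SBRT shrinks it enough: 70 mm with a 30% reduction gives 49 mm, then 59 mm after ablation, +20.4%.

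**Sensitivity**
- *Zone shrinkage by fraction f.* (d + 10)(1 - f) ≥ 1.2d gives d ≤ 10(1 - f)/(0.20 + f). The limit is 44.5 mm at 2%, 40.0 mm at 4%, 38.0 mm at 5% and 30.0 mm at 10%. The relative limb is the binding one at all these limits.
- *Tumour change g between nadir scan and ablation.* d ≤ (10 + g)/0.20: 40 mm for g = -2, 45 mm for -1, 55 mm for +1, 60 mm for +2.
- *Second target lesion.* A 41 mm renal lesion plus a 10 mm lesion gives 10/51 = 19.6%, not progression.
- *Achieved margin.* At m mm per side with no shrinkage, d ≤ 2m/0.20: 40 mm for m = 4, 60 mm for m = 6. For m = 7, the limit is 70 mm with no shrinkage, 53 mm with 5% (13.3/0.25) and 42 mm with 10% (12.6/0.30).
- *Volume, assuming a sphere.* 41 to 51 mm is (51/41)³ = 1.92, or +92%. With 10% shrinkage of the zone diameter it is (45.9/41)³ = 1.40, or +40%.

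**Scale in Phase IB.** Each misclassified patient among ten moves a simple rate by 10 percentage points. As an illustration, two false failures turn 10/10 (exact 95% CI 69-100%) into 8/10 (44-97%).

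**The case against.** The strongest reply is that nothing in the protocol tells the reader to count ablated tissue outside the tumour as target lesion. Section 7.2 measures the target lesion, and Section 6.5 itself separates the tumour from the margin. That stands: progression follows only on one of two possible readings. It does not close the gap, because measuring enhancing tissue alone would also be a rule the protocol does not contain.

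The second reply is fragility, and it stands too. Within the eligible size range the zone clears the progression limit by at most 1.8 mm. At 4% shrinkage by the 3-month scan, no nadir above 40 mm qualifies. But the sensitivity runs both ways, since a margin above 5 mm raises the limit. A classification that turns on a millimetre or two of procedural geometry is a poor measure of tumour control in either direction.

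A reader might infer more than the documents support:
- *That every successful ablation up to 5 cm meets the progression rule at the first follow-up scan.* This needs all the assumptions listed in the working, and the protocol states none of them.
- *That these patients also become PFS events.* The PFS event is an undefined recurrence, not RECIST progression.
- *That a named local-failure rule misfires.* Section 9.4.2.1 names no failure category; the event is undefined.
- *That error is concentrated in smaller tumours and good SBRT responders.* The geometry points that way, but it depends on the same assumptions, and the protocol gives no SBRT response rate by 4-6 weeks.

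The empty MWA cell in Table 2 is not an error in itself: that row covers chest, abdomen and pelvis, and Section 6.5 already specifies the procedural CT.

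**Conclusion.** The point holds in conditional form and should be fixed. The protocol compares post-ablation diameters with a pre-ablation nadir, aims for a zone larger than the tumour, and does not say what is measured or from which scan. If the whole zone is measured, a technically successful ablation can be classed as progression for a nadir sum up to 50 mm, under the assumptions in the working. That limit is a calculation for one set of conditions, not a prediction for the trial. A separate consequence needs no growth threshold: complete response cannot be met while a measured zone persists.

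The reach is limited to local control, a secondary and descriptive endpoint, and to PFS only if recurrence is read as RECIST progression. DLT, dose escalation and the MTD are unaffected. The point still matters because local control is the estimate to be carried into Phase II planning.

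**What to change.** In Sections 7.2 and 9.3.2.1:
1. Use RECIST from the pre-SBRT baseline to the 4-6 week scan to describe SBRT response only.
2. After MWA, take a new reference for the ablated lesion from the post-procedure contrast CT in Section 6.5, or from the first post-ablation scan if contrast is not given. State what is measured.
3. Define local failure as growth of at least 20% and 5 mm over the smallest post-ablation measurement, or new or enlarging enhancing tissue in or at the edge of the zone. The enhancement limb is a proposal; the documents contain no such criterion. The reference should be a running nadir: a 60 mm zone that shrinks to 40 mm would have to reach 72 mm against a fixed reference (1.2 × 60), but 48 mm against its nadir (1.2 × 40).
4. Define recurrence for PFS in the same way for the treated lesion, and keep RECIST for other lesions and new lesions.

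The cost is protocol wording and one measurement on a scan already taken. SBRT response and post-ablation control become two reported quantities. The reference scan will differ for patients who cannot have contrast, so the report should say how many they are. The wording should be settled before any post-ablation scan is scored; scans already read can be re-measured.

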9.0 Statistical Analysis

9.1 Number of patients

9.1.1 Phase IA – Nine (9) – eighteen (18) patients

9.1.1.1 We estimate that approximately 40-50 potentially eligible patients are seen at UWCCC each year. With a 3+3 study design and an estimated 20% rate of enrollment, we estimate it will take 1-2 years for patient accrual, treatment, and followup for determination of toxicity of the initial 9-18 patient Phase IA cohort.

9.1.2 Phase IB – Ten (10) patients

9.1.2.1 An additional ten patient, Phase IB expansion cohort will be accrued at the MTD at the conclusion of the Phase IA study to obtain further assessments of safety and provide preliminary estimates of local control rates to inform a potential Phase II study.

9.2 Study Endpoint(s)

- 9.2.1 Primary Endpoint of Phase I study:
 - 9.2.1.1 Dose-limiting toxicity with SBRT combined with microwave ablation for renal cell carcinoma.
- 9.2.2 Secondary Endpoint(s) of Phase I study:
 - 9.2.2.1 Local control rate
 - 9.2.2.2 Progression free survival
 - 9.2.2.3 Overall survival
 - 9.2.2.4 Tumor pathology of post-SBRT specimen

9.3 Definition of end-points

- 9.3.1 Primary Endpoint of the Phase I study:

Dose-limiting toxicity (DLT) will be defined as grade 4 or higher non-hematologic toxicity attributable to treatment occurring until 30 days after ablation. This will exclude toxicities not caused by treatment, such as pain due to tumor progression. Toxicities will be defined per NCI CTCAE v5.0.

- 9.3.2 Secondary endpoints of the Phase I study:
 - 9.3.2.1 Local control: Radiologic response per RECIST criteria and volumetric measurements.
 - 9.3.2.2 Progression free survival defined with follow-up radiological assessment with progression free survival (PFS) calculated from the point of start of SBRT to the point of recurrence or death.
 - 9.3.2.3 Overall survival (OS) defined from the point of start of SBRT to the time of death or last follow-up if alive.
 - 9.3.2.4 Tumor pathology: H&E staining and pathologic evaluation for percentage of viable tumor remaining as measured by the presence of necrosis, fibrosis, hyalinization, and/or calcification, compared to pre-SBRT pathology.

9.4 Statistical Analysis

- 9.4.1 Primary objective of Phase I study:

A 3+3 design will be utilized for dose escalation. For each three patient cohort, DLT will be assessed as above. In the case of 0/3 DLTs, the dose will be escalated to the next level. In the case of 2/3 DLTs, the trial will be terminated with the previous level being the MTD. In the case of 1/3 DLTs, an additional three patients will be enrolled at the current dose level. If no additional DLTs are seen, the dose will be escalated to the next level. In the event of a total of 2 or more DLTs in 6 patients, the trial will be terminated with the previous dose level being the MTD. Toxicities will be tabulated by type and grade.

- 9.4.2 Secondary objectives of Phase I study:

- 9.4.2.1 Local control will be reported actuarially as a percentage with an associated 95% exact confidence interval.
- 9.4.2.2 Progression free and overall survival will be estimated using the Kaplan-Meier method. For calculation of PFS, patients without recurrence and alive at last follow-up will be censored at the date of the last radiologic assessment. For calculation of OS, patients alive at last follow-up will be censored. Log-rank test and Cox regression analysis will be used for univariate and multivariate analyses, respectively. Chi-square and regression analysis will be performed to test association of categorical variables with treatment response.
- 9.4.2.3 Tumor response will be reported via rates of complete response, partial response, and no response.

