One challenge that exists when utilizing high doses of radiation therapy in the kidney is that of respiratory induced tumor motion. Respiratory gating techniques are utilized to minimize normal tissue irradiation. Nevertheless, any such technique is limited by the fact that it depends on the assumption that there is a good correlation between respiratory motion and tumor motion.

The recent emergence of a radiation treatment system allowing real-time MRI imaging during treatment may obviate the dependence on respiratory gating techniques[13]. Tracking tumor motion in real time allows the potential for the delivery of safe and effective radiation treatment with the goal of improving control rates of ablative treatments for large, medically inoperable renal cell carcinomas.

We propose a Phase I study to determine the feasibility of adding SBRT treatment for patients undergoing treatment for RCC. We hope to show that such treatment is feasible and safe.

3. Study Objectives

- 3.1 Working hypothesis – We hypothesize that the addition of SBRT treatment to microwave ablation is safe and can be delivered without undue toxicity.
- 3.2 Primary Objective - The primary objective of this study is to determine the maximum tolerated dose (MTD) of stereotactic body radiation therapy followed by microwave ablation for non-operable renal cell carcinoma. Toxicity will be evaluated via the CTCAE Criteria v5.0. Expected side effects of radiation treatment include potential fatigue, dermatitis, chest wall pain, nausea, and hematuria. Side effects of ablation may include hemorrhage, treatment site pain, urinary retention, and a decrease in glomerular filtration rate.
- 3.3 Secondary Objective - The secondary objectives of this study include estimation of rates of local control, progression-free survival, overall survival, and tumor response on biopsy.
- 3.4 Exploratory Objective – To assess pathologic response after stereotactic body radiation therapy and immune cell infiltrate.
- 3.5 Study Duration – We estimate that approximately 40-50 potentially eligible patients are seen at UWCCC each year. With a 3+3 study design and an estimated 20% rate of enrollment, we estimate it will take 1-2 years for patient accrual, treatment, and followup for determination of acute toxicity of the initial 9-18 patient Phase IA cohort. This cohort will then be followed for a period of 3 years, giving an estimated study duration of 5 years.

4. Selection of Patients

- 4.1 Inclusion Criteria

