6.7 Duration of Therapy

Treatment with SBRT will be delivered over a period of two weeks, with radiation delivered two to three times per week. Four to six weeks after treatment, patients will be evaluated for microwave ablation by the treating radiologist with repeat CT or MRI imaging of the abdomen. Eight weeks after the conclusion of radiation treatment, patients will undergo microwave ablation, a single procedure. Adjuvant systemic treatment will be administered per institutional policies, physician recommendations, and patient preferences. Criteria for removal from study are described below.

6.8 Duration of Follow-Up: Refer to Table 2

After study enrollment, patients will undergo SBRT over a period of approximately 2 weeks. After 8 weeks, patients will undergo microwave ablation. Post treatment, patients will be followed as per standard of care. This will include a clinical visit four weeks after ablation, three months after ablation, six months after ablation, followed by visits every 6 months for a period of 3 years. Imaging will include either contrast-enhanced CT or MRI imaging at 3 and 6 months post therapy and every 6 months for 3 years. A BMP (including creatinine) will be obtained with imaging to evaluate renal function. Long term toxicity (specifically, nephrotoxicity, bowel obstruction, skin changes, and pain) will be assessed at these follow-up visits. Follow-up visits will be conducted by one of the treating physicians (radiation oncologist, interventional radiologist, or urologist) who will document physical exam, laboratory, and imaging findings as well as evaluate for toxicity. Any other evaluations prompted by symptoms, laboratory evaluation, or at the treating physicians' discretion may be performed as per standard of care. If a patient decides to withdraw from the study for non-treatment related reasons, no additional study-specific information will be obtained from the patient's future follow-up visit.

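### The PFS rule counts a death at any time but censors living patients at their last scan, with no time limit, so the late curve is biased downward if deaths are counted after scanning stops

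*Combined protocol and SAP*

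**What the plan says.** PFS is "calculated from the point of start of SBRT to the point of recurrence or death" (9.3.2.2; 7.3 has the same definition), with no limit on when a death counts. For patients who have not had an event, 9.4.2.2 says that "patients without recurrence and alive at last follow-up will be censored at the date of the last radiologic assessment". The estimator is stated there too: "Progression free and overall survival will be estimated using the Kaplan-Meier method". No cut-off date, truncation time or missed-scan rule is given.

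The text on what happens after year 3 does not agree:

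- Section 6.8: "Imaging will include either contrast-enhanced CT or MRI imaging at 3 and 6 months post therapy and every 6 months for 3 years". Nothing is listed after that.
- Section 8.1: "Patients will be followed for a minimum of three years with standard-of-care clinical visits, laboratory studies, and imaging". Once three years have passed, "further follow-up will be at the discretion of the treating physician".
- Table 2, footnote 2: visits continue annually after 3 years, in the column that carries the imaging mark.
- Table 2, footnote 5: all imaging after ablation is at the physician's discretion, in line with NCCN guidelines.

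Section 3.5 plans 3 years of follow-up for the Phase IA cohort, "giving an estimated study duration of 5 years". OS (7.4, 9.3.2.3) runs to death or last follow-up, with no cap.

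**The concern.** Kaplan-Meier needs censoring that does not depend on the outcome. Under this rule, time lived after the last scan counts only for a patient who goes on to die. A patient last scanned at month 38 and alive without recurrence at month 55 leaves the risk set at 38. One last scanned at month 38 who dies without recurrence at month 50 stays in it until 50. Beyond the last scan, the risk set is therefore made up of future deaths.

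Patients are medically inoperable and metastatic disease is allowed, so deaths without documented recurrence after year 3 are plausible. PFS is a named secondary endpoint, and at most 28 patients will contribute, so one or two such deaths could determine the tail of the curve and any median read from it.

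**Working it through.** The plan states no PFS rate, event count or power for PFS, so there is no figure to reproduce. The rule itself can be tested.

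**Inputs from the documents**

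- Last scheduled scan under 6.8: 2 weeks of SBRT + 8 weeks to ablation = 10 weeks, about 2.3 months; 2.3 + 36 is about 38 months from SBRT start.
- Accrual (3.5, 9.1.1.1): 20% of 40-50 patients = 8-10 per year; 9 is used below.
- Study duration: 5 years = 60 months (3.5).
- Maximum size: 18 + 10 = 28 (6.2.4).

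**Example by hand.** Take 28 patients: 10 PFS events by month 38, deaths without recurrence at months 45 and 52, and 16 patients alive at month 60.

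| Handling | After month 38 | After month 45 | After month 52 |
|---|---|---|---|
| As written, no scan after month 38 | 18/28 = 0.643 | 0.643 × 1/2 = 0.321 | 0.321 × 0/1 = 0 |
| As written, annual scan at about month 50 | 0.643 | 0.643 × 17/18 = 0.607 | 0.607 × 0/1 = 0 |
| Living patients kept at risk to month 60 | 0.643 | 0.607 | 0.607 × 16/17 = 0.571 |
| PFS ended at the last scheduled scan | 0.643 | 0.643 | 0.643 |

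Two deaths among 18 event-free patients take the curve from 0.643 to zero. An annual scan postpones the drop but does not remove it, because a death after that scan again faces a risk set of one.

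**Simulation.** The documents give no event rates, so these are assumed: progression 10% per year, and death without progression 5% or 10% per year, taken as constant and independent. Entry is 9 per year, the data cut is at 60 months, and N is 18 or 28. Progression is dated at the first scan after it occurs.

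True PFS at 48 months is exp(-(0.10 + 0.05) × 4) = 0.55, or exp(-(0.10 + 0.10) × 4) = 0.45. For N = 28 with no scans after year 3, the rule as written averages about 0.45 and 0.31, which is 10 and 14 points below truth. Censoring living patients at last contact gives about 0.60 and 0.49, so the rule is about 15-18 points below that comparator. Last-contact censoring runs high because it misses progression that no scan has picked up. N = 18 gives similar results.

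| After year 3 | Trials in which the curve reaches zero |
|---|---|
| No scans, deaths counted to month 60 | about 37-57% |
| Annual scan, deaths counted to month 60 | about 7-15% |
| Follow-up ends at about month 38 | about 1% |

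Up to about 38 months the estimate is essentially unbiased when scans run on schedule. If they lapse earlier, as footnote 5 permits, the asymmetry starts earlier: with an assumed 30% per year dropping out of scanning, 36-month PFS fell 4-7 points below truth.

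**The case against.** The strongest objection is that two conditions must both hold before the late curve is damaged: scans stop, and deaths go on being counted. A reader might infer that scanning ends at 3 years and the curve is bound to collapse. The documents do not support that. Footnote 2 continues visits annually, footnote 5 leaves imaging to discretion, and 8.1 calls three years a minimum. Nor does any section provide for collecting deaths from all causes after year 3. The absence of a cap on OS follow-up is silence, and collection of related serious adverse events during the study ends at the latest three years after ablation (13.4). If follow-up simply stops at about 38 months, the problem almost disappears. This stands, and it makes the finding conditional. It does not remove the finding, because the plan leaves both conditions open.

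A reader might also take a larger size, up to 23 points at 48 months and a zero curve in 73% of trials. That requires all 28 patients to have at least 38 months of follow-up. Phase IB opens only after Phase IA (9.1.2.1). With entry at 9 per year, only those who enter in the first 60 - 38 = 22 months can have 38 months of follow-up by month 60, or 9 × 22/12, about 16-17 patients. The stated accrual and duration do not support the larger figures.

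Nor does a log-rank result become biased downward: the test has no such direction, and a death in a risk set of one adds nothing to it (observed equals expected, variance zero). What is biased is the curve, and any median or late landmark read from it.

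Finally, PFS is secondary. Section 9.5.1 rests the move to Phase II on safety and powers that study on local control. This limits the consequence.

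**Conclusion.** The point holds in conditional form. The asymmetry and the missing time limit are in the text of 9.3.2.2 and 9.4.2.2 and rest on no assumption. The harm to the late curve needs deaths to be counted after a patient's scans have stopped, which the plan neither provides for nor rules out.

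The sizes above rest on assumed event rates and an assumed pattern of post-year-3 scanning and death collection, and should be read as a range. The worst supported case is a curve about 10-14 points too low at 48 months that often ends at zero; the mildest is no material effect. PFS to about 3 years is sound if scans are done on schedule, and dose escalation and the MTD are untouched. The rule should be corrected before analysis, but it does not threaten the primary objective.

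**What to change.** In 9.4.2.2:

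1. Analyse PFS only up to a fixed time from SBRT start that matches the end of scheduled imaging: about 38 months under 6.8, set so that it includes the final scheduled scan and its visit window. Patients event-free at that time are censored at their last scan on or before it.
2. Within that period, count a death as a PFS event only if it falls within a prespecified interval of the last adequate scan (for example, two scheduled scan intervals). Otherwise censor at that scan.
3. Apply both rules to patients who do not receive MWA. This is why the limit runs from SBRT start and not from a post-ablation visit.
4. Count all deaths for OS. Report PFS at 12, 24 and 36 months with numbers at risk.

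Reconcile 6.8, 8.1 and Table 2 footnotes 2 and 5 on imaging after 3 years, and state whether deaths are collected after that point. If the reconciled schedule changes when imaging ends, the PFS limit should follow it.

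The cost is a few sentences, with no new visits or data. There would be no PFS estimate beyond scheduled imaging, and some deaths after lapsed scanning would count for OS only. The interval rule limits the asymmetry for patients whose scans lapse early but does not remove it entirely.
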